**SYNOPSIS**

[figure not shown]
Master Protocol Title:	Platform of R andomized A daptive C linical T rials In C ritical Illness (PRACTICAL) Randomized Control Trial
Domain Protocol Title:	The Corticosteroid Early and Extended (CORT-E) RCT
Patient States:	This domain will enrol patients in the following platform defined states; 
 
• Non-intubated patients;
 
• Intubated patients, not on extracorporeal life support, with low normalized respiratory system elastance (<2.5 cm H2O/(ml/kg predicted body weight));
 
• Intubated patients, not on extracorporeal life support, with high normalized respiratory system elastance (≥2.5 cm H2O/(ml/kg predicted body weight));
 
• Patients on extracorporeal life support.
 

Domain Arms:	The arms being studied in this domain are: 
Early Cohort
 
 
- Intervention arm – Early corticosteroid use in patients with AHRF
 
- Control arm – Usual care without corticosteroids
 
 
Extended Cohort
 
 
- Intervention arm – extending corticosteroid use (for another 10 days) in AHRF patients still requiring invasive or non-invasive respiratory support after receiving 10 days of corticosteroids
 
- Control arm – Usual care without extending corticosteroids
 

Hypothesis	Early corticosteroids will improve survival (Early Cohort) in patients with AHRF; and extending corticosteroids (Extended Cohort) will improve survival in those with AHRF still requiring invasive or non-invasive respiratory despite already receiving 10 days of corticosteroids.
Domain Primary Outcome:	60-day mortality from the day of randomization

[figure not shown]

Domain Secondary Outcome:
	
 
1. Mortality at other endpoints (ICU/hospital discharge, 30 days and 6 months)
 
2. Hospital length of stay
 
3. Duration of NIV
 
4. Duration of supplemental oxygen use
 
5. Ordinal scale of daily respiratory support
 
6. Need for ECLS
 
7. Duration of ECLS (for those that require ECLS)
 
8. Ventilator-free days (VFDs) censored at day 30
 
9. Health-related quality of life at 6 months (measured with EQ-5D)
 
10. Complications from Corticosteroids: 
 
a. Hyponatremia (serum sodium > 150 mmol/L)
 
b. Hyperglycemia (requiring new insulin or increase in insulin by >30% from initial/baseline dose)
 
c. Delirium
 
d. Clinically important GI bleeding (requiring endoscopy or RBC transfusion)
 
e. Nosocomial infection
 
f. Neuromuscular weakness
 
 
 

Domain Design:
	
A phase III, interventional, open-label, randomized, multi-site study

Duration:
	
2.5 years of accrual and 6 months follow-up for a total study duration of approximately 3 years.

Planned Total Sample Size:
	
The Bayesian approach does not require a fixed sample size as the trial will continue enrolling until a statistical trigger is met (see section Sample Size for additional details). It is estimated that a maximum of 2000 patients will be enrolled in each cohort at 30 to 40 sites.

Inclusion/Exclusion Criteria:	
Patients will be eligible for enrolment in this domain if they meet the PRACTICAL platform eligibility criteria and the criteria specific to either cohort in the CORT-E domain.
 
PRACTICAL Inclusion Criteria
 
1) Acute hypoxemic respiratory failure meeting all of the following criteria;
 

a) New or worsening respiratory symptoms developing within 2 weeks prior to the onset of need for oxygen or respiratory support

b) Receiving any of the following types of oxygen or respiratory support for at least 4 hours prior to the time of randomization; supplemental oxygen at 10 L/min or higher, high flow nasal oxygen (at any flow rate),

--------------------------------------	--

[figure not shown]

	
non-invasive ventilator support, invasive ventilator support, or extracorporeal life support (ECLS)
 
c) <math>FiO_2 \geq 0.40</math> (for venturi mask, high flow nasal cannula, or invasive or non-invasive ventilation) or oxygen flow rate <math>\geq 10</math> L/min on face mask for at least 4 hours at the time of evaluation for eligibility unless already on extra-corporeal life support
 
2) Age <math>\geq 18</math> years
 
PRACTICAL Exclusion Criteria
 

1. Hypoxemia is primarily attributable to acute heart failure or fluid overload

2. Hypoxemia is primarily attributable to pulmonary embolism

3. Hypoxemia is primarily attributable to status asthmaticus

4. Extubation is planned or anticipated on the day of screening

5. ICU discharge is planned or anticipated on the day of screening

6. The patient is moribund and deemed unlikely to survive past 24 hours (as determined by the clinical team)

7. The patient is being transitioned to a fully palliative philosophy of care

 
CORT-E Domain Eligibility Criteria
 
Early Cohort:
 
Inclusion Criteria
 

1. Within 72 hours of admission to an ICU

2. New unilateral or bilateral airspace disease

 
Exclusion Criteria
 

1. Receiving only low flow oxygen therapy less than or equal to 15L/min

2. More than two doses of corticosteroids (oral or IV, at any dose) received any time during the previous 14 days prior to screening

3. Existing indication for corticosteroids

4. High suspicion for/confirmed COVID infection

5. Acute traumatic brain injury during the index hospital admission

--	---

[figure not shown]

	
6. Allergy to dexamethasone
 
Extended Cohort:

--	--

	
Inclusion Criteria
 
 
1. Are admitted to an ICU
 
2. Have already received a short course (defined below) of corticosteroid specifically for acute respiratory failure, this will include patients:             
 
a. randomized to corticosteroid arm in Early Cohort and completed 10 days of corticosteroid as per Early Cohort protocol
 
b. patients with COVID who have received between 8-12 days of corticosteroids as standard of care
 
c. others who have received between 8-12 days of corticosteroids for AHRF
 
 
 
 
OF NOTE: the initial corticosteroid does not have to be dexamethasone and corticosteroids can be at any initial dose
 
 
3. Ongoing AHRF requiring HFNC, NIV (continuous positive airway pressure [CPAP] or bilevel) or invasive ventilation
 
 
Exclusion Criteria
 
 
1. An alternate indication for ongoing corticosteroids
 
2. Acute traumatic brain injury this hospital admission.
 

Study Assessments:	Study assessments are depicted in the Study Schema section.
Safety Variables & Analysis:	The safety and tolerability of corticosteroid administration will be evaluated by recording frequency and type of serious adverse events in both groups.
Statistical Analysis:	All analyses, interim and final, will use the intention-to-treat principle. The baseline characteristics comparing randomized groups will be reported using means (and standard deviations), medians (and interquartile ranges) or proportions. Trial data will be analyzed using Bayesian hierarchical generalized linear models to estimate the posterior probability of superiority (or inferiority) and equivalence for each intervention within each cohort. Additional details on statistical analysis are included in section Analyses and the PRACTICAL Master Statistical Analysis Plan (SAP).

[figure not shown]

---

---

[figure not shown]

---

---

[figure not shown]
**LIST OF ABBREVIATIONS**

ABG	Arterial Blood Gases
AE	Adverse Event
AHRF	Acute Hypoxemic Respiratory Failure
ARDS	Acute Respiratory Distress Syndrome
CAP	Community acquired pneumonia
CCCTG	Canadian Critical Care Trials Group
CIHR	Canadian Institutes of Health Research
CORT-E2	Corticosteroid Early and Extended
COVID	Coronavirus Disease
CPAP	Continuous Positive Airway Pressure
CRF	Case Report Form
DSMB	Data Safety Monitoring Board
ECLS	Extracorporeal Life Support
ECMO	Extracorporeal Membrane Oxygenation
HFNC	High Flow Nasal Cannula
ICU	Intensive Care Unit
IRB	Institutional Review Board
NIV	Non-Invasive Ventilation
PaCO 2	Partial pressure of carbon dioxide
PaO 2	Partial pressure of Oxygen
PEEP	Positive End Expiratory Pressure
REB	Research Ethics Board
RCT	Randomized Controlled Trial
SAE	Serious Adverse Events

---

SAP	Statistical Analysis Plan
SCCM	Society of Critical Care Medicine
SDM	Substitute Decision Maker
SOC	Standard of Care
SpO 2	Percent Saturation of Oxygen

## **BACKGROUND**

[figure not shown]
Complete background information of the Platform of Randomized Adaptive Clinical Trials in Critical Illness (PRACTICAL) Randomized Control Trial can be found in the Master Protocol.

### **The Problem to be Addressed**

AHRF is a clinical syndrome defined by the development of acute hypoxemia requiring respiratory support with high flow nasal cannula (HFNC), non-invasive ventilation (NIV), invasive ventilation, or extracorporeal life support (ECLS). AHRF is caused by varying etiologies, including COVID and non-COVID-related (such as aspiration, bacterial pneumonia, trauma, sepsis), and is common, affecting about 15% of all ICU patients and >30,000 Canadians annually with mortality ranging between 20% and 50% depending on severity of illness. Survivors of AHRF experience increased healthcare utilization and costs in the year following ICU admission. AHRF results from altered permeability of the alveolar capillary membrane due to systemic and pulmonary inflammatory/immune responses, and is essentially synonymous with acute respiratory distress syndrome (ARDS). However, different from ARDS, AHRF does not require the presence of bilateral airspace opacities on chest imaging, which has proven to be poorly reproducible, and does not mandate intubation, thereby including a large proportion of patients requiring noninvasive methods of oxygen support such as HFNC. In fact, two quadrant infiltrate in the same lung (not meeting ARDS criteria) and two quadrant infiltrate in different lungs (meeting ARDS criteria) have almost identical outcomes. Given this and the challenges with recognizing ARDS, clinicians and researchers are increasingly focused on the more pragmatically defined and recognizable syndrome of AHRF, reflected by a growing number of RCTs focused on this population.

#### Early Cohort – Early Corticosteroids in non-COVID AHRF

Given the profound inflammatory response associated with AHRF, various immune modulators, have been evaluated as potential treatment options. A meta-analysis of 7 RCTs in 1703 COVID patients with AHRF, which included RECOVERY (Randomized Evaluation of COVID-19 Therapy) data, showed a reduction in mortality with the use of corticosteroids (odds ratio [OR] 0.66, 95% confidence interval [CI] 0.53 to 0.82). The 7 RCTs used various regimens with different formulations, doses and durations of therapy. These results informed a WHO living guideline, coauthored by members of our team, which provided a strong recommendation for corticosteroids in patients with COVID-related AHRF. Whether these results from COVID studies are generalizable to non-COVID AHRF patients is unknown.

[figure not shown]
To address this question, our group performed a meta-analysis of 18 RCTs examining the role of corticosteroids in ARDS of any etiology (see Appendix). Pooled analysis suggested that corticosteroids probably reduce 28-day mortality (relative risk [RR] 0.82, 95% CI 0.72 to 0.95, moderate certainty) and may reduce the duration of mechanical ventilation (mean difference [MD] 4.0 days, 95% CI 2.5 to 5.5 days fewer, low certainty), with an uncertain effect on corticosteroid-related complications such as neuromuscular weakness, gastrointestinal bleeding and metabolic derangements. These findings were consistent across both COVID and various non-COVID etiologies of ARDS. Despite our findings, corticosteroid use in non-COVID AHRF remains highly variable. Of note, the recently published CAPE-COD RCT demonstrated improved outcomes with corticosteroids in patients with severe CAP. A large, robust, multicentre RCT, enrolling non-COVID AHRF patients, including patients who are receiving non-invasive and invasive oxygen support, is needed to address whether non-COVID patients with AHRF will benefit from early corticosteroid therapy.

#### Extended Cohort – Extended Corticosteroids in COVID or non-COVID AHRF

As part of our meta-analysis, we examined a number of pre-defined subgroups including dose, timing, and molecule. Of the subgroups, only duration of corticosteroid therapy demonstrated credible effect modification, with patients who received longer courses (> 7days) experiencing lower mortality compared to those who received shorter courses (<= 7 days) (p-value for interaction = 0.04, moderate credibility of subgroup effect) with no evidence to suggest an increase in adverse events with the longer duration.

The duration of therapy subgroup finding is interesting, given that, despite ubiquitous use of corticosteroids in COVID AHRF, uncertainty persists regarding optimal duration. Although most clinicians follow the RECOVERY protocol of 10 days, this duration was arbitrary. Throughout the pandemic, clinicians have struggled with the decision of what to do when a patient is not improving at the end of the 10-day treatment window, with persistent AHRF requiring invasive or non-invasive respiratory support. We have argued (published review describing the principles guiding corticosteroid therapy in AHRF) based on corticosteroid plasma concentration-time profiles and pharmacodynamic studies that optimal response may require a prolonged course of corticosteroids longer than 10 days. The question regarding optimal duration, especially in those with persisting AHRF, is relevant to all patients regardless of the etiology of their AHRF. A large, multicentre RCT, enrolling AHRF patients with persisting respiratory failure despite an initial course of corticosteroids, is needed to address whether extended corticosteroids in this population impacts outcomes.

[figure not shown]
## Why This Study Is Needed

This clinical trial is designed to inform clinical practice and address two knowledge gaps in COVID and non-COVID respiratory failure.

**Early Cohort** – *There is uncertainty whether lessons learned from corticosteroids in COVID AHRF are generalizable to non-COVID AHRF.* The DEXA-ARDS trial randomized 277 critically ill patients with non-COVID ARDS to receive dexamethasone 20mg daily or placebo and found a reduction in mortality (-15.3%, 95% CI -4.9 to -25.9%) and an increase in ventilator-free days at 28 days (MD 4.8 days more, 95% CI 2.57 to 7.03 days more) with dexamethasone. A 2015 meta-analysis suggested that corticosteroids reduced mortality in patients with severe community-acquired pneumonia (RR 0.67, 95% CI 0.45 to 1.01). Despite these data suggesting benefit of corticosteroids in non-COVID AHRF, use of this therapy remains highly variable. The 2017 Society of Critical Care Medicine (SCCM) guidelines made a conditional recommendation for corticosteroids in both ARDS and CAP based on moderate certainty evidence, with a rationale that further high quality data was needed before a strong recommendation could be made.

***Patients with non-COVID AHRF, not meeting traditional ARDS criteria, but receiving HFNC or NIV may benefit from corticosteroids but have not been sufficiently studied.*** Use of HFNC has increased markedly in patients with AHRF. In fact, the most recent 2020 European guideline made a strong recommendation for HFNC in patients with AHRF. We are aware of planned updates to the ARDS definition that will include patients on HFNC. Studies evaluating the effect of corticosteroids in critically ill COVID patients demonstrated a trend towards greater effect of corticosteroids in those requiring HFNC or NIV compared to invasive mechanical ventilation (ratio of ORs 4.34, 95% CI 1.46 to 12.91) with the hypothesis that modulating the inflammatory response early before it becomes too severe may be optimal. Corticosteroids also reduce the need for invasive mechanical ventilation in patients with COVID AHRF (25 fewer per 1000, 95% CI 1 to 44 fewer). It is unclear whether these lessons learned from COVID AHRF are generalizable to non-COVID AHRF patients on HFNC or NIV.

**Extended Cohort** - *The benefit of corticosteroids in COVID AHRF is substantial; however the optimal duration of treatment is unknown. This issue is also unresolved for non-COVID AHRF.* Despite availability of effective vaccines, ICUs worldwide are continuing to see patients with AHRF from COVID, due to new variants, vaccine hesitancy, and host vulnerability. Although corticosteroids have become ubiquitous for treatment of COVID AHRF, the optimal duration of therapy remains unclear, especially in those with non-resolving disease. COVID patients with progressive clinical deterioration and ongoing requirement for life support have higher persisting

[figure not shown]
levels of inflammatory biomarkers and therefore continuing corticosteroids beyond 10 days could lead to important benefits. The question related to optimal duration in those with persisting AHRF, is relevant to all patients, including both COVID and non-COVID AHRF. Answering this question is a global priority and has the potential to improve outcomes for millions of patients who develop AHRF each year.

### **Safety of Intervention**

[figure not shown]
Although corticosteroid administration has been associated with potential harms (e.g. immunosuppression, metabolic derangements, obesity, osteoporosis, gastric ulceration, etc.) these adverse effects are generally associated with durations of therapy over 1 month. The RECOVERY trial did not show an increased risk of serious adverse events in patients randomized to dexamethasone compared to those that did not receive corticosteroid. Our meta-analysis examining corticosteroids in all patients with ARDS found corticosteroids probably increase hyperglycemia (RR 1.11, 95% CI 1.01 to 1.23, moderate certainty) with an uncertain effect on neuromuscular weakness (RR 0.85, 95% CI 0.62 to 1.18, very low certainty) and GI bleeding (RR 1.20, 95% CI 0.43 to 3.34, low certainty). Duration of corticosteroid therapy among included studies ranged from 5 to 30 days, with the majority (10/18) using a duration of 14 days or longer. In general, metabolic changes associated with short-term corticosteroid administration are easily treated in the ICU setting. Although there is no demonstrated increased risk of nosocomial infection associated with short-course corticosteroids in critically ill patients, this is an ongoing concern and therefore this will be carefully captured and adjudicated as part of the CORT-E trial.

### **Domain Set-Up**

The Corticosteroid Early and Extended (CORT-E) Trial is a phase III, multicentre Bayesian randomized controlled trial (RCT), embedded within the PRACTICAL platform trial (refer to the Master Protocol), which includes two cohorts within the domain; early corticosteroids in AHRF (Early Cohort) and extended corticosteroids in persisting AHRF (Extended Cohort). Patients enrolled in the Early Cohort may be eligible for randomization into the Extended Cohort after they have completed their corticosteroid treatment as part of the Early Cohort. Figure 1 below provides a flow-chart summary of the structure of the domain.

[figure not shown]
**Figure 1:** CORT-E Study Schema

\*Includes COVID, CAP, etc

## Summary

The results of the CORT-E trial may change the management of patients with AHRF in ICUs worldwide. Lessons learned from this trial will impact both COVID and non-COVID patients, with large-scale applicability irrespective of the pandemic waning or evolving. Compared to many interventions, corticosteroids are inexpensive and easily administered. Thus, if early corticosteroids in AHRF or extended corticosteroids prove beneficial, operationalizing their use will be straightforward. If no difference is seen, our results will still be very informative and support not using corticosteroids in early non-COVID AHRF and using for only short durations (10 days) in those with COVID or other conditions for which corticosteroids are used.

---

---

## PRIMARY RESEARCH QUESTIONS, HYPOTHESIS, AND STUDY OUTCOMES

### Primary Research Questions

**Early Cohort:** In patients with AHRF not already treated with corticosteroids who are requiring HFNC, NIV, invasive ventilation or ECLS, what is the effect of 10 days of dexamethasone compared to no dexamethasone on 60-day mortality?

**Extended Cohort:** In patients with AHRF of any etiology who have been treated with approximately 10 days of corticosteroids, and who have ongoing requirement for HFNC, NIV, invasive ventilation, or ECLS, what is the effect of extending therapy with dexamethasone for another 10 days compared to stopping dexamethasone on 60-day mortality ?

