##### **Extended Cohort**

##### Inclusion Criteria

1. Are admitted to an ICU
2. Have already received a short course (defined below) of corticosteroid specifically for acute respiratory failure, this will include patients:

- a. randomized to corticosteroid arm in Early Cohort and completed 10 days of corticosteroid as per Early Cohort protocol
  - b. patients with COVID who have received between 8-12 days of corticosteroids as standard of care
  - c. others who have received between 8-12 days of corticosteroids for AHRF
- OF NOTE: the initial corticosteroid does not have to be dexamethasone and corticosteroids can be at any initial dose
3. Ongoing AHRF requiring HFNC, NIV (continuous positive airway pressure [CPAP] or bilevel) or invasive ventilation

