corticosteroid prescription (e.g., if only 8 or 9 days were prescribed) or practicalities (e.g., to avoid weekends or holidays). If there is uncertainty as to whether corticosteroids were prescribed for AHRF or another indication, the treating team should be consulted to confirm eligibility.

Sites will maintain a screening log documenting all patients reviewed and reasons for exclusion.

Eligible and consented patients for either cohort will be randomized via REDCap, following a 1:1 (intervention arm: control arm) schedule stratified by study centre and level of oxygen support (non-invasive, invasive or ECLS) at the time of randomization.

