## TRIAL INTERVENTIONS

### Early Cohort

#### Intervention Arm:

[figure not shown]
Patients randomized to receive corticosteroids will receive dexamethasone 20mg daily for 5 days and then 10mg for an additional 5 days, for a total of 10 days or until ICU discharge or death, whichever comes first. After 10 days dexamethasone will be stopped without a taper. If a patient is discharged from the ICU prior to completing the protocol, then ongoing corticosteroid management will be up to the treating team as per SOC.

Dexamethasone will be administered parenterally (intravenous administration). Specific details on the timing of administration are provided below;

- 20mg dexamethasone is to be administered as soon as possible and on the day of randomization (Day 0), and this dose will be administered daily for a total of 5 days of treatment (Day 0 – Day 4). Then, the dexamethasone dose will be reduced to 10mg and this dose will be administered daily for a total of 5 days (Day 5 – Day 9).
- In rare cases where it is not possible to administer the first dose of study drug on the same day as randomization (e.g., if the patient is randomized very close to midnight), 20 mg dexamethasone can be started the day following randomization (Day 1), and will be administered daily for a total of 5 days of treatment (Day 1 – Day 5). Then, the dexamethasone dose will be reduced to 10mg and this dose will be administered daily for a total of 5 days (Day 6 – Day 10).

Patients finishing 10 days of dexamethasone as part of the Early Cohort will be eligible for randomization in the Extended Cohort if they are still requiring HFNC, NIV, IMV or ECLS, and according to the other eligibility criteria for the Extended Cohort.

**Control Arm:** Those randomized to usual care will receive routine AHRF management without corticosteroids. All other aspects of care will be at the discretion of the treating team including antibiotics, intravenous fluids, mechanical ventilation and ECLS.

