**Extended Cohort**

**Intervention Arm:** Patients randomized to receive extended dexamethasone will receive dexamethasone 10mg for an additional 10 days. At the end of the additional 10 days, the dexamethasone dose will be halved to 5mg for another 5 days (to reduce the risk of adrenal insufficiency) and then stopped (including taper, a total of 23-27 days (depending on the length of their initial course of dexamethasone [8-12 days]) or until ICU discharge or death, whichever comes first). A taper is encouraged, however not mandated even if the patient is sent to the ward. If a patient is discharged from the ICU prior to completing the protocol, then ongoing corticosteroid management will be up to the treating team as per SOC.

Dexamethasone will be administered parenterally (intravenous administration). Specific details on the timing of administration are provided below;

- Dexamethasone is to be administered such that there is no lapse in dexamethasone treatment (no dexamethasone free day in between their last dose from Early Cohort or SOC and their first day of dexamethasone treatment as part of the Extended Cohort).
- If the patient is randomized the day after they received their last dexamethasone dose as part of the Early Cohort or SOC; 10mg dexamethasone will be administered on the day of randomization (Day 0) and this dose will be administered daily for a total of 10 days of treatment (Day 0 – Day 9). Then, the dexamethasone dose will be reduced to 5mg and this dose will be administered daily for a total of 5 days (Day 10 – Day 14).
- If the patient is randomized on the same day they are receiving their last dexamethasone dose as part of the Early Cohort or SOC; 10mg dexamethasone will be administered on the next day (Day 1) and this dose will be administered daily for a total of 10 days of treatment (Day 1 – Day 10). Then, the dexamethasone dose will be reduced to 5mg and this dose will be administered daily for a total of 5 days (Day 11 – Day 15).

**Control Arm:** Those randomized to the comparator arm will stop corticosteroids after their initial course without a taper. All other aspects of care will be directed by the treating team.

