### **Analyses**

Any deviation from the original statistical plan will be described in the final report.

[figure not shown]

All analyses, interim and final, will use the intention-to-treat principle. The baseline characteristics comparing randomized groups will be reported using means (and standard deviations), medians (and interquartile ranges) or proportions. Trial data will be analyzed using Bayesian hierarchical generalized linear models to estimate the posterior probability of superiority (or inferiority) and equivalence for each intervention within each domain. The hierarchical model will account for centre, time period, sex and oxygen support at the time of randomization (HNFC, NIV, invasive mechanical ventilation or ECLS). Posterior probability distributions will be computed by combining the likelihood function with minimally informative priors and updated every three months as information (observations) accumulate in the trial. Statistical analysis will be adjusted for whether a patient was enrolled in one CORT-E cohort or both CORT-E cohorts. We do not expect interaction between CORT-E and the other PRACTICAL domains. The final study analysis, separate for each cohort, will be completed once either superiority, inferiority or equivalence has been observed and confirmed by the DSMB and Platform Steering Committee.

We will collect sex and perform subgroup analysis based on this variable. It is less feasible to collect gender as most patients will not be conscious at the time of enrolment. We don't expect effect modification for either cohort based on sex or gender. Understanding the CORT-E eligibility criteria, we plan to enroll a diverse population of patients representative of the demographics of ICU patients presenting at the participating sites.

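### The Early Cohort question is worded as 10 days of dexamethasone versus none, but its intention-to-treat contrast estimates a strategy that includes randomised extension, and the planned one-versus-both adjustment does not recover the 10-day effect

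*Protocol*

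**What the plan says.** Protocol, Primary Research Questions, Early Cohort: "what is the effect of 10 days of dexamethasone compared to no dexamethasone on 60-day mortality". Under Trial Interventions, Early Cohort, the steroid course stops after 10 days without a taper, and for controls "Those randomized to usual care will receive routine AHRF management without corticosteroids".

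The same section continues: "Patients finishing 10 days of dexamethasone as part of the Early Cohort will be eligible for randomization in the Extended Cohort", provided they still need support and meet that cohort's other criteria. The Extended Cohort inclusion criteria name the route from Early as patients "randomized to corticosteroid arm in Early Cohort and completed 10 days of corticosteroid as per Early Cohort protocol". Patient Randomization sets both randomisations "following a 1:1 (intervention arm: control arm) schedule". Under Trial Interventions, Extended Cohort, the intervention arm "will receive dexamethasone 10mg for an additional 10 days", then a 5-day taper. Treatment ends sooner at ICU discharge or death, and the taper is encouraged but not mandated.

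Analyses: "All analyses, interim and final, will use the intention-to-treat principle". That section also adjusts for whether a patient entered one cohort or both, without saying which cohort's model this applies to. The one-versus-both subgroup is listed for the Extended Cohort only. Under Sample Size, stopping is decided separately in each cohort.

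**The concern.** The question names a fixed 10-day course. The arm analysed under intention-to-treat mixes patients who got at most 10 days of protocol dexamethasone with some who got up to 25. The extra treatment is given between about day 10 and day 25 of Early follow-up, so it can affect Early 60-day mortality.

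The Hypothesis section predicts that extension improves survival. If so, the Early estimate looks better than the 10-day effect; if extension harms, it hides part of that effect. If the Extended Cohort stops first, the mixture also changes partway through Early enrolment.

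The only stated handling is the one-versus-both adjustment. In the Extended model that variable is fixed before randomisation and is harmless. In the Early model it is a consequence of treatment allocation and of surviving to day 10 with persisting failure.

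**Working it through.** **1. Course length.** The protocol's stated total of 23-27 days reproduces: 8 + 10 + 5 = 23 and 12 + 10 + 5 = 27. From Early it is 10 + 10 + 5 = 25 days, so at most 15 beyond the 10 in the question.

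**2. Carry-over into the Early contrast.** The protocol gives no control mortality for the design (only a background range of 20-50%), no share re-randomised and no extension effect. Assumed: control mortality 35%; share of the steroid arm re-randomised f = 15%, 25% or 40%; mortality in those allocated to stop m = 35% or 45%; extension OR 0.75 or 1.33.

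- Planned effect at OR 0.75: odds 0.35/0.65 × 0.75 = 0.4038, risk 28.8%, a difference of 6.2 points.
- Shift in steroid-arm risk = f × 0.5 × (risk with extension − m).
- Example: f = 0.40, m = 0.45, extension OR 0.75. Risk with extension is 0.380; shift = 0.40 × 0.5 × (0.380 − 0.450) = −1.4 points; steroid-arm risk = 28.8 − 1.4 = 27.4%; OR = 0.70.

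| True 10-day OR | Extension OR 0.75: Early OR reads | Extension OR 1.33: Early OR reads |
|---|---|---|
| 0.75 | 0.70-0.73 | 0.77-0.80 |
| 1.00 | 0.94-0.98 | 1.02-1.06 |

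For extension OR 0.75 the shift is 0.5-1.4 points, or 8-22% of the 6.2-point effect. With extension OR 1.0 it is zero.

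**3. Effect on the superiority trigger.** The stated triggers were simulated with looks at 750 patients and every 200 after that, up to 2000, with a flat prior and normal approximation. Here f was 10-40%, control mortality 30-40% and m 45%. With a true 10-day OR of 1.0 and extension OR 0.75, superiority is declared in 4-10% of trials, against about 3% when extension has no effect. Such a result is wrong for the 10-day question, not for the strategy. These figures are for the contrast without the one-versus-both covariate.

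**4. The one-versus-both covariate in the Early model.** If dual enrolment occurs only in the steroid arm, the treatment coefficient is set by single-cohort patients: the steroid-arm patients not re-randomised against all controls. Take a full null with 35% mortality overall and 45% in re-randomised patients (assumed). Risk in the steroid-arm remainder = (0.35 − 0.45f)/(1 − f), compared with control odds 0.35/0.65 = 0.538.

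| f | Risk in remainder | OR (true value 1.00) |
|---|---|---|
| 20% | 0.26/0.80 = 32.5% | 0.89 |
| 30% | 0.215/0.70 = 30.7% | 0.82 |
| 40% | 0.17/0.60 = 28.3% | 0.73 |

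A logistic regression on 400,000 simulated patients gave 0.90, 0.83 and 0.73.

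**5. Follow-up clock.** A footnote to the Study Assessment Schema runs the day-60 check for dual-enrolled patients from the second randomisation, at about day 70 of Early, and does not require it twice. Early outcomes for these patients must be counted from the Early date; the text does not say that they will be.

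**6. Precision of a 10-day analysis.** With weight 2 for patients re-randomised to stop, 0 for those re-randomised to extend and 1 for all others, write p = 0.288 for 10-day mortality and r = (p − fm)/(1 − f) for risk in those not re-randomised. Per-patient steroid-arm variance is (1 − f)[r(1 − r) + (r − p)²] + 2f[m(1 − m) + (m − p)²], against p(1 − p) unweighted. Dividing each by [p(1 − p)]² and adding 1/(0.35 × 0.65) for controls gives a log-OR variance ratio of 1.09 (f = 15%, m = 35%) to 1.28 (f = 40%, m = 45%).

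**The case against.** The strongest reply is that intention-to-treat from the first randomisation validly answers whether to start steroids early. The Synopsis and Hypothesis describe the Early intervention without a fixed duration. The overlap between cohorts is deliberate and disclosed: Domain Set-Up describes it and Minimizing Sources of Bias uses it to justify the open-label design. This stands. The strategy is a legitimate estimand; the fault is that the research question names a different one, and that the stated adjustment targets neither.

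A supplementary estimator would normally sit in the SAP. That is fair, but the question, the re-randomisation and the adjustment are all written in this protocol and conflict there.

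The shift is also small. With 2000 patients the standard error of the log OR is about 0.096; reading 0.70-0.73 for 0.75 moves the log OR by 0.02-0.07, less than one standard error.

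A reader might infer more than the protocol supports:

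- **That half of all steroid-arm patients still supported at day 10 are extended.** Only half of those eligible, consenting and re-randomised are. Planned extubation, planned ICU discharge, palliative transition and an alternate steroid indication all exclude.
- **That everyone extended gets 15 more days.** That is a maximum.
- **That Early controls can never enter.** The Extended criteria admit others with 8-12 days of corticosteroids for AHRF, so a control given open-label steroids could enter, though the protocol expects few crossovers.
- **That steroid complications in the Early arm are inflated.** This is not shown; the Background reports no evidence of more adverse events with longer courses.

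**Conclusion.** The concern holds as a mismatch between the question and the estimand, made worse by an unsuitable covariate. The Early intention-to-treat contrast estimates early dexamethasone with 1:1 randomised extension in eligible, consenting patients still supported, against usual care. It does not estimate the 10-day effect unless extension has no effect.

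The carry-over is unknown because the share re-randomised is not given, and it is modest over the assumed range. The covariate can do more harm: its bias does not need extension to work, only that re-randomised patients have a different risk from the rest of their arm. If the adjustment is meant for the Extended model alone, the protocol should say so.

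It does not follow that the primary Early analysis is invalid, or that conclusions on early steroids and the stopping triggers should move to a weighted estimate. The design's operating characteristics were not simulated for that estimate.

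**What to change.** 1. Keep intention-to-treat as the primary Early analysis, and state in Primary Research Questions and Analyses that it estimates the strategy actually compared: early dexamethasone, with randomised extension for eligible patients still supported, versus usual care.
2. Remove the one-versus-both covariate from the Early model. It may stay in the Extended model.
3. Pre-specify a supplementary weighted Early analysis of 60-day mortality for the 10-day question: weight 2 if re-randomised to stop, 0 if re-randomised to extend, 1 otherwise. The weights use the known allocation probability of 1/2. Count outcomes from the Early randomisation date, including for dual-enrolled patients.
4. Report the weighted result beside the primary one whenever a conclusion is drawn about a 10-day course. Leave the stopping triggers on the primary analysis.

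Cost: wording changes and one extra analysis, with variance about 9-28% larger than the primary under the assumptions above. No extra patients are needed.
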